## 6.2 Weekly Study Drug Infusion

During the placebo-controlled treatment period, all participants will receive a weekly infusion of study drug (trehalose or placebo for 60 + 10 minutes, participants who require more than 2 bags of SLS-005 the infusion time is to be increased to 90 + 10 minutes) for the first 4 weeks of the study in clinic. Thereafter home infusions can be considered if the participant has had no adverse reaction to the infusion and all safety assessments are within acceptable limits.

During the Week 8 in-clinic visit, PK assessments will occur prior to and after the infusion per the SOA. Therefore, if a participant transitions to home infusions after the first four weeks the site should coordinate the Week 8 infusion to occur in-clinic while the participant is in for the Week 8 in-clinic visit. The home infusion nurse will not collect any PK samples; therefore, the Week 8 PK samples would be missed if the Week 8 infusion does not occur in-clinic at the time of the Week 8 in-clinic visit. This would not result in a protocol deviation.

Concurrent assessments such as vital signs, reporting of any infusion related adverse events, and reporting of new concomitant medications is to be completed weekly in conjunction with the study drug infusion.

Blood pressure, respiration rate, and heart rate, should be conducted at four timepoints during each infusion: (1) Pre-dose, (2) midway through infusion = 30  $\pm$  5 min post start of infusion, (3) end of infusion = 60  $\pm$  10 min post start of infusion, and (4) 90  $\pm$  10 min post start of infusion. If a participant requires a 90-minute infusion duration due to receiving more than 2 bags of study drug an additional vital signs measurement is to be completed approximately 30 minutes ( $\pm$  10 mins) after the end of infusion.

*\*If a participant requires a 90-minute infusion duration due to receiving  $>2$  bags of study drug an additional vital signs measurement should be done 30 minutes ( $\pm 10$  min) after the end of infusion.*

Abbreviations: IV = intravenous

If the infusion is done at home, confirmation of infusion and information on infusion-related adverse events, and changes in health and medications will be provided to study site by the home infusion nurse via study provided source documents. Site staff will then enter the data into the EDC and follow up with the participant as needed to document any changes in AEs or concomitant medications in the EDC.

### 6.3 Week 2 Telephone Visit

This visit will take place  $14 \pm 3$  days after the Baseline Visit. No regimen-specific procedures will be performed at this visit.

If the participant will receive their in-clinic infusion within the Week 2 visit window, this visit may occur in-clinic at the time of the infusion visit.

### 6.4 Week 4 and 8 Visits

Study drug should not be administered until *after* all study visit procedures are complete.

These visits will take place on Days  $28 \pm 7$  and  $56 \pm 7$  days, respectively. The following procedures will be performed for the regimen schedule:

- Collect urine, *prior to start of infusion*. If urine cannot be collected prior to infusion, no urine should be collected at this visit
- Collect safety labs
- CNS Bulbar Function Scale [Week 8 only]

- Adjustment of dosing volume based on most recent weight measurement as necessary
- Administer infusion of study drug in clinic after all study procedures have been completed, provided at least 4 days have passed since prior infusion.
- During each infusion, vital signs associated with the infusion (systolic and diastolic pressure, respiratory rate, and heart rate) are to be measured pre-infusion, 30 minutes ( $\pm 5$  mins) after the start of infusion (SOI), at the end of infusion ( $\pm 10$  mins), and 90 minutes ( $\pm 10$  mins) after the start of infusion. If a participant requires a 90-minute infusion duration due to receiving more than 2 bags of study drug an additional vital signs measurement is to be completed approximately 30 minutes ( $\pm 10$  mins) after the end of infusion.
- For applicable participants, collect PK blood sample (Pre-dose, 1-hour  $\pm 5$  minutes, 2 hours  $\pm 5$  minutes, and 4 hours  $\pm 5$  minutes post start of infusion) [Week 8 only]

#### 6.4 Week 12 Telephone Visit

This visit will take place  $84 \pm 3$  days after the Baseline Visit. No regimen-specific procedures will be performed at this visit.

If the participant will receive their infusion in clinic and within the Week 12 visit window, this visit may occur in-clinic at the time of the infusion visit.

#### 6.5 Week 16 Visit

Study drug should not be administered until after study visit procedures are complete.

This visit will take place on Day  $112 \pm 7$  days. The following procedures will be performed for the regimen schedule:

- Document participant's willingness to participate in the OLE
  - If OLE consent is not obtained at Week 16, it may be obtained at Week 24.
- CNS Bulbar Function Scale
  - Collect safety labs including for HbA1c evaluation
  - Collect urine, *prior to start of infusion*. If urine cannot be collected prior to infusion, no urine should be collected at this visit
- Adjustment of dosing volume based on most recent weight measurement as necessary
- Administer infusion of study drug in clinic after all study procedures have been completed, provided at least 4 days have passed since prior infusion.
  - During each infusion, vital signs associated with the infusion (systolic and diastolic pressure, respiratory rate, and heart rate) are to be measured pre-infusion, 30 minutes ( $\pm 5$  mins) after the start of infusion (SOI), at the end of infusion ( $\pm 10$  mins), and 90 minutes ( $\pm 10$  mins) after the start of infusion. If a

participant requires a 90-minute infusion duration due to receiving more than 2 bags of study drug an additional vital signs measurement is to be completed approximately 30 minutes ( $\pm 10$  mins) after the end of infusion.

### 6.6 Week 20 Telephone Visit

This visit will take place  $140 \pm 3$  days after the Baseline Visit. No regimen-specific procedures will be performed at this visit.

If the participant will receive their infusion in clinic and within the Week 20 visit window, this visit may occur in-clinic at the time of the infusion visit.

### 6.7 Week 24 Visit or Early Termination Visit

Study drug should not be administered until after study visit procedures are complete.

This visit will take place on Day  $168 \pm 7$  days. The following procedures will be performed for the regimen schedule:

- ALSAQ-40
- CNS Bulbar Function Scale
- Collect urine, *prior to start of infusion*. If urine cannot be collected prior to infusion, no urine should be collected at this visit
- Collect safety labs including for HbA1c evaluation
- Adjustment of dosing volume based on most recent weight measurement as necessary (only if participant is continuing in the Open Label Extension)
- Administer infusion (**Drug is only administered at this visit if the participant is continuing in the Open Label Extension.**)
- During each infusion, vital signs associated with the infusion (systolic and diastolic pressure, respiratory rate, and heart rate) are to be measured pre-infusion, 30 minutes ( $\pm 5$  mins) after the start of infusion (SOI), at the end of infusion ( $\pm 10$  mins), and 90 minutes ( $\pm 10$  mins) after the start of infusion. If a participant requires a 90-minute infusion duration due to receiving more than 2 bags of study drug an additional vital signs measurement is to be completed approximately 30 minutes ( $\pm 10$  mins) after the end of infusion.
  - Note: The first OLE infusion should occur in-clinic following completion of the Week 24 visit. The participant's final infusion of the placebo-controlled treatment period should be scheduled and completed at least 4 days prior to the Week 24 Visit.

### 6.8 Follow-Up Safety Call

Participants will have a Follow-Up Safety Call  $28 \pm 3$  days after their last dose of study drug. Only those participants NOT continuing on in the Open Label Extension will have the Follow-Up Safety Call following the end of their participation in the placebo-controlled portion of the trial.

The following procedures will be performed:

- Assess and document AEs

### **6.9 Process for Early Terminations**

Participants who early terminate from the study and do not complete the protocol per ITT will be asked to be seen for an in-person Early Termination Visit and complete a Follow-Up Safety Call.

The in-person Early Termination Visit should be scheduled as soon as possible after a participant early terminates. If the participant early terminates during the placebo-controlled portion of the Regimen, all assessments that are collected at the Week 24 in-clinic visit should be conducted. The Follow-Up Safety Call should be completed approximately 28 days after the last dose of study drug.

If the Early Termination Visit occurs approximately 28±3 days after the last dose of study drug, the information for the Follow-Up Safety Call can be collected during the Early Termination Visit, and a separate Follow-Up Safety Call does not need to be completed. If the in-person Early Termination Visit does not occur within 28±3 days of the last dose of study drug, the Follow-Up Safety Call should occur approximately 28 days after the last dose of study drug and the Early Termination Visit will be completed after the Follow-Up Safety Call.

If a participant decides to discontinue study drug, but will complete the protocol per ITT, an in-person Early Termination Visit and Follow-Up Safety Call is not necessary.

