#### **Follow-up Duration**

At the conclusion of the 24-week placebo-controlled treatment period of the study, all participants will either schedule a 28-day follow up phone call and end their participation in the

regimen or have the option to receive intravenous infusions of trehalose in the Open Label Extension (OLE) period of the study. The duration of the OLE period is planned for 52 weeks.

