### **Total Planned Trial Duration**

For participants completing the placebo-controlled treatment period of the study, the planned amount of time for a participant in the trial is up to 34 weeks, or about 8 months. This duration assumes a 6-week screening window, a 24-week placebo-controlled treatment period, and a 4-week safety follow-up period for those participants who do not enter the OLE. Participants will complete approximately 10 study visits during the placebo-controlled treatment period of the study, in addition to weekly infusions outside of these visits.

If the participant opts into the subsequent OLE, the total planned amount of time for a participant in the trial is approximately 86 weeks. This duration assumes a 6-week screening window, 24-week placebo-controlled treatment period, a 52-week OLE period, and a 4-week safety follow-up period. Participants will complete 10 study visits across the planned 52-week OLE period of the study, in addition to weekly infusions outside of these visits.

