- 5 During each infusion, vital signs associated with the infusion (systolic and diastolic pressure, respiratory rate, and heart rate) are to be measured pre-infusion, 30 minutes ( $\pm 5$  mins) after the start of infusion (SOI), 60 minutes after the start of infusion ( $\pm 10$  mins), and 90 minutes ( $\pm 10$  mins) after the start of infusion. If a participant requires a 90-minute infusion duration due to receiving more than 2 bags of study drug an additional vital signs measurement is to be completed approximately 30 minutes ( $\pm 10$  mins) after the end of the 90-minute infusion.
- 6 Clinical safety labs include hematology (CBC with differential), complete chemistry panel, thyroid function and urinalysis. Hb A1C will be included in labs at baseline, week 16 and week 24. Serum pregnancy testing will occur in women of child-bearing potential at the Master Protocol Screening Visit and as necessary during the study. Pregnancy testing is only repeated as applicable if there is a concern for pregnancy.
- 7 Adverse events that occur after signing the master protocol consent form will be recorded.
- 8 The DNA sample can be collected after the Baseline Visit if a baseline sample is not obtained or the sample is not usable.
- 9 Administer first dose of study drug only after Baseline Visit procedures are completed.
- 10 Participants will only have a Follow-Up Safety Call at this time if they *do not* continue on in the OLE. Participants who continue into OLE will have a Follow-Up Safety Call after their last dose of investigational product during the OLE period.
- 11 Vital status, defined as a determination of date of death or death equivalent or date last known alive, will be determined for each randomized participant at the end of the placebo-controlled portion of their follow-up (generally the Week 24 visit, as indicated). If at that time the participant is alive, his or her vital status should be determined again at the time of the last patient last visit (LPLV) of the placebo-controlled portion of a given regimen. We may also ascertain vital status at later time points by using publicly available data sources as described in section 8.15 of the Master Protocol.
- 12 If the CSF collection is unable to be performed for logistical reasons, such as scheduling, at the Week 16 Visit, it may be performed at the Week 24 Visit.

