#### **3.2 End of Participation Definition**

A participant is considered to have ended his or her participation in the placebo-controlled period of the Regimen if they:

- Complete planned placebo-controlled period visits, as described in the SOA, including participants on or off study drug
- Early terminate from the study and complete the Early Termination Visit and Follow-Up Phone call as described in Section 6.9
- Withdraw consent to continue participation in the study, or are lost to follow-up

If a participant initiates open-label study drug in the OLE period, he or she is considered to have completed his or her participation in the OLE period of the Regimen if they choose to discontinue participation or if all planned OLE period visits, including the last visit or the last scheduled procedure shown in the SOA, have been completed.

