## 5.7 Participant Compliance

Participants should be encouraged not to miss infusions if at all possible, as it may affect the efficacy of the drug. The dosing window is 1 week  $\pm$  3 days. There should be no fewer than 4 days between study drug infusions.

Compliance will be automatically calculated in the EDC for each weekly infusion.

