## 5.9 Overdose

Certain safety events that occur in association with investigational product may require reporting. These safety events include, but are not limited to, the following:

- Overdose of the investigational product, where ‘overdose’ is defined as  $> 125\%$  of the intended dose for a single treatment day infusion.
- Suspected abuse/misuse of the investigational product
- Inadvertent or accidental exposure to the investigational product
- Medication error involving study drug (with or without participant exposure to the investigational product, e.g., name confusion)
- The half-life of Trehalose Injection 90.5 mg/mL is approximately 1.5 hours, and there is no antidote. Trehalose is metabolized to 2 glucose molecules, there are no other metabolites. Supportive care with monitoring of vital signs, blood glucose levels, and liver enzymes should be considered. In 1 subject who received 81 g of Trehalose Injection 90.5 mg/mL, there was an increase in liver enzyme levels, but liver function remained normal and liver enzyme values returned to normal without treatment.

These safety events should be reported to the Coordination Center whether they result in an AE/SAE or not. Safety events associated with an AE/SAE should also be reported in the EDC. The SI should also contact the Medical Monitor within 24 hours of the SI’s awareness.

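### Protocol 6.9, read literally, waives the 28-day safety call for every on-study drug-stopper whatever the last-dose date; only late stoppers lose follow-up, and one sentence would fix it

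*Protocol*

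**What the plan says.** Four places in the protocol describe safety follow-up after the last dose.

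- **Follow-up Duration:** after the 24-week period, "all participants will either schedule a 28-day follow up phone call and end their participation in the" regimen, or they have the option of the OLE.
- **Total Planned Trial Duration:** the total includes "a 4-week safety follow-up period for those participants who do not enter the OLE".
- **Section 6.8:** the call is made 28±3 days after the last dose, for participants not continuing into the OLE. No exception is made for people who stopped drug. Footnote 10 of the Schedule of Activities limits the call to the same group: "Participants will only have a Follow-Up Safety Call at this time if they" do not go on to the OLE.
- **Section 6.9, last sentence:** for a participant who stops study drug but remains in the study, "will complete the protocol per ITT, an in-person Early Termination Visit and Follow-Up Safety Call is not necessary".

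Two other provisions bear on who is affected. Section 3.2 lists as one way of ending participation: "Complete planned placebo-controlled period visits, as described in the SOA, including participants on or off study drug". Sections 4.4 and 6.10 open the OLE to those who complete the placebo-controlled period on study drug, so drug-stoppers appear to be in the group that section 6.8 covers.

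**The concern.** The last sentence of 6.9 names the safety call and removes it regardless of when the last infusion was given. A site following that sentence would skip a call that 6.8 requires, while a site following 6.8 would make it.

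The same section already has a suitable safeguard for people who leave the study. Their separate call is dropped only if the Early Termination Visit falls about 28±3 days after the last dose. Drug-stoppers who stay have no such test. Someone last dosed on Day 154 who leaves the study is followed to about Day 182 (154 + 28). Someone last dosed on the same day who stays could have a final AE review on Day 168.

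At stake is the length of the AE window for people who stop infusions late, some of them possibly because of an AE. On-drug completers outside the OLE would be followed for longer.

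**Working it through.** **Inputs.** Infusions are weekly with a ±3 day window (section 5.7), so nominal infusions fall on Days 0, 7, …, 161. Week 24 is Day 168±7 (section 6.7), and the "final infusion of the placebo-controlled treatment period should be scheduled and completed at least 4 days prior to the Week 24 Visit". The call is due 28±3 days after the last dose (section 6.8), so the shortest conforming follow-up is 28 − 3 = 25 days. AE review is scheduled at every visit and call (Schedule of Activities).

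**The plan's own figure.** 6 weeks of screening + 24 weeks of treatment + 4 weeks of safety follow-up = 34 weeks, as stated. With the OLE, 6 + 24 + 52 + 4 = 86 weeks, also as stated. The 34-week total includes the four weeks that 6.9 appears to waive.

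**Follow-up if the call is skipped.** Days of AE follow-up = Week 24 visit day − last-dose day. For a Day 168 visit:

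- Last dose Day 140: 168 − 140 = 28 days, no gap. Earlier last doses leave more.
- Last dose Day 147: 168 − 147 = 21 days, short.
- Last dose Day 154: 168 − 154 = 14 days, short. The lost tail is 28 − 14 = 14 days.

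A Day 161 last dose is the normal final infusion, so that person is not a drug-stopper and gets the call under 6.8.

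**Share of last-dose days affected.** A stopper is someone whose last dose precedes the normal final infusion. The documents give neither a stopping rate nor its timing. I assume that 10–30% of the 160 participants stop drug and stay on study, with timing uniform over the dosing days. People affected = 160 × (0.10 to 0.30) × share.

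| Week 24 visit | Final infusion | Possible last-dose days | Short last doses (days of follow-up) | Share | People affected |
|---|---|---|---|---|---|
| Day 168 | Day 161 | 23 (0 to 154) | Day 147 (21), Day 154 (14) | 2/23 = 8.7% | 1.39 to 4.17 |
| Day 161 | Day 154 | 22 (0 to 147) | Day 140 (21), Day 147 (14) | 2/22 = 9.1% | 1.45 to 4.36 |
| Day 175 | Day 161 | 23 (0 to 154) | Day 154 (21) | 1/23 = 4.3% | 0.70 to 2.09 |
| Day 175 | Day 168 | 24 (0 to 161) | Day 154 (21), Day 161 (14) | 2/24 = 8.3% | 1.33 to 4.00 |

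If one omitted final infusion counts as a missed dose and not a stop, the Day 168 row becomes 1/22 = 4.5%, or 0.73 to 2.18 people. The Day 161 row becomes 1/21 = 4.8%, or 0.76 to 2.29. The counts are the same with a 25-day or a 28-day threshold. The ±3 day dosing window is not modelled.

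**Clinical scale.** "The half-life of Trehalose Injection 90.5 mg/mL is approximately 1.5 hours", so 14 days is 14 × 24 / 1.5 = 224 half-lives.

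**The case against.** The strongest reply is that nothing conflicts. The sentence closes a section on early terminations, whose opening pairs an Early Termination Visit with a safety call for people who leave. Naming the same pair again, it may say only that stopping drug does not trigger that package. Section 3.2 supports this: early terminators follow 6.9, while others complete the scheduled visits on or off drug, and the Schedule of Activities has its own safety-call column. SAP section 6.7.1 likewise lists only a safety follow-up visit or the OLE after Week 24. This reading is plausible, but 6.9 does not state it, and its plain words remove the call.

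Other replies stand in full.

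- A last dose on Day 154 before a Day 168 visit is one omitted infusion. Section 5.7 treats missed infusions as a compliance matter ("Participants should be encouraged not to miss infusions if at all possible"), so this may not be a discontinuation at all.
- The protocol does not say that one or two missed infusions bar OLE entry, and OLE entrants are owed no call at that point.
- The count includes placebo participants. For the 120 planned on active drug it is 120 × (0.10 to 0.30) × 2/23 = 1.0 to 3.1.
- The call collects only AEs. Week 24 still collects AEs and safety labs, and vital status is checked again at the last patient's last visit.

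A reader might infer that every drug-stopper loses 28-day follow-up. The visit schedule shows otherwise. A reader might also infer that AEs would drop out of the safety analysis, because SAP section 6.6.1 names no clear end of the treatment-emergent interval for a living completer off drug who has no safety call and does not enter the OLE. That text does not exclude an AE recorded at Week 24, and it modifies the Master SAP, which was not available and may supply the rule. This is at most a wording clarification.

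**Conclusion.** The concern holds in a narrow form. Read literally, 6.9 waives the safety call without a last-dose condition and conflicts with Follow-up Duration, Total Planned Trial Duration and section 6.8 for participants outside the OLE. The intent may have been narrower.

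The effect is confined to the last one or two nominal dosing slots. With a Day 168 visit, follow-up is 21 or 14 days where 28±3 is intended. The figure of about 1 to 4 people depends entirely on the assumed stopping rate and timing. Clinical weight is low given the short half-life and the Week 24 assessments, and no efficacy result changes.

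The Master Protocol was not available. It might show the intent, but SAP section 1 ranks this regimen appendix above it on non-statistical matters, so it would not override the sentence in 6.9. Confidence is medium because of the alternative reading.

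**What to change.** In section 6.9, waive the separate call for on-study drug-stoppers only when a scheduled visit or call with AE review falls at least 25 days after the last dose. Otherwise make the existing call under 6.8. With a Day 168 visit, last doses up to Day 140 would stay waived. A Day 147 last dose would need a call on Day 175±3, and a Day 154 last dose on Day 182±3.

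If the sentence was meant only to say that the early-termination package does not apply, saying so and pointing to 6.8 would resolve the conflict.

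The cost is one sentence in the protocol and a few phone calls by existing site staff, about 1 to 4 under the stated assumptions. Stating the end of the treatment-emergent interval for this group in SAP 6.6.1 is an optional clarification, subject to the Master SAP, and the fix does not depend on it.
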